6.2. Handling of Dropouts or Missing Data

Missing data, except dates, will not be imputed. Historical data such as historical diagnosis, historical illness, preexisting conditions and prior therapies should be collected in a sufficiently informative way. For example, in order to be considered as historical illness, events occurring in the same year as study entry should have at least a known month and year for the end date, while events occurring in previous years should have at least a known year for the end date. The start

dates and end dates for adverse events and concomitant medications will be imputed following the most recent Sponsors' standards. Partial dates should be reported in all listings and not the imputed date.

6.3. Patient Disposition

A detailed summary of patient disposition will be provided. It will include a summary of the number and percentage of patients entered into the study, and treated as well as number and percentage of patients completing the study (patients who receive 1 cycle of study dose or are evaluable for DLT for Phase 1a and patients who have at least 1 postbaseline tumor assessment for Phase 1b), or discontinuing (overall and by reason for discontinuation of LY3475070). Reason for discontinuation from both the study treatment and the study will be summarized by predetermined categories.

A listing of primary reasons for study treatment and study discontinuation will also be provided.

6.4. Patient Characteristics

Patient demographics (including age, sex, screening height, weight, body mass index, race, ethnicity, and country) will be reported using descriptive statistics. The summary will include the number of patients for each treatment group and the total across treatment groups.

The following baseline disease characteristics will be summarized by treatment arm: Eastern Cooperative Oncology Group (ECOG) performance status, initial pathological diagnosis, and basis of initial pathological diagnosis.

Patient preexisting condition, historical illness, prior anti-cancer therapies, and other baseline characteristics such as biomarker and genetic alterations at baseline will be summarized as deemed appropriate.

6.5. Treatment Compliance

Study treatment compliance will be assessed as the proportion of treatment that is actually taken, relative to what is expected, after accounting for protocol-defined dose adjustments. Study treatment taken will be derived from the difference between the total number of capsules/tablets dispensed and returned over the course of the patient's treatment. The number of cycles received, dose omissions, dose reductions, dose delays, and dose intensity will be summarized for all treated patients by treatment arm.

6.6. Concomitant Therapy

All medications will be coded to the generic preferred name according to the current World Health Organization (WHO) drug dictionary. All concomitant medications will be summarized for the safety population using the preferred name.

6.7. Efficacy Analyses

The antitumor activity of LY3475070 monotherapy and in combination with pembrolizumab will be assessed based on RECIST 1.1 and iRECIST (Seymour et al. 2017), respectively. The

efficacy analyses will be focused on treated participants (safety populations) in Phase 1a part of the study (dose escalation), and in Phase 1b part of the study (dose expansion).

The Kaplan-Meier method (Kaplan and Meier 1958) will be used to estimate the curves, median time and 95% CI of time to event parameters such as OS, PFS and DoR based on RECIST 1.1, iPFS and iDOR based on iRECIST for each arm of Cohorts C and D, and Cohort E. Overall response rate (ORR based on RECIST 1.1 and iORR based on iRECIST), with corresponding 95% exact CI, will be summarized for each arm of Cohorts C and D, and Cohort E. ORR with corresponding 95% exact CI will also be summarized for the monotherapy and combination cohorts in Phase 1a part of the study.

The following definitions for efficacy endpoints will be used:

Primary Endpoint

Overall response rate (ORR) is defined as the number of patients who achieve a best overall response of complete response (CR) or partial response (PR) divided by the total number of patients treated (safety population). The ORR, with 95% CI, will be summarized for each study part.

Secondary Endpoints

The **disease control rate (DCR)**, defined as the proportion of patients who achieved a CR or PR or stable disease (SD) out of all patients treated, will also be summarized. Best response is determined from a sequence of responses assessed. Two objective status determinations of CR before progression are required for a best response of CR. Two determinations of PR or better before progression, but not qualifying for a CR, are required for a best response of PR.

Duration of response (DoR) is defined as the time from the date measurement criteria for CR or PR (whichever is first recorded) are first met until the first date that disease is recurrent or objective progression is observed, per RECIST 1.1 criteria, or the date of death from any cause in the absence of objectively determined disease progression or recurrence. Duration of SD will be calculated only for patients with best response of SD. It is measured from the date of start of treatment to the date of first progression of disease or the date of death due to any cause, whichever is earlier. For each patient who is not known to have died or to have had a progression of disease as of the data-inclusion cut-off date, duration of SD will be censored at the date of last objective response assessment prior to the date of any subsequent systemic anticancer therapy.

Progression-free survival (PFS) is defined as the time from the date of start of treatment to the first date of the observed clinical or radiologically documented PD or death due to any cause, whichever occurs first. For patients who are not known to have died or progressed as of the data-inclusion cut-off date, PFS time will be censored at the date of the last objective progression-free disease assessment prior to the date of any subsequent systematic anticancer therapy.

PFS Event/Censoring Scheme

Situation ^a	Event/Censor	Date of Event or Censor
Tumor progression or death	Event	Earliest date of PD or death
No tumor progression and no death	Censored	Date of last adequate tumor assessment per RECIST 1.1, or date of first dose (whichever is later) ^b
Unless		
No baseline radiologic tumor assessment available	Censored	Date of first dose
No adequate postbaseline tumor assessment available and death reported after 2 scan intervals following the first dose ^{b, c}	Censored	Date of first dose
Tumor progression or death documented immediately after 2 or more scan intervals following last adequate tumor assessment or randomization (whichever is later) ^{b, c}	Censored	Date of last adequate tumor assessment, per RECIST 1.1, or date of first dose (whichever is later) ^b
New therapeutic anticancer treatment started prior to tumor progression or death	Censored	Date of last adequate radiological assessment prior to new therapeutic anticancer therapy ^b

Abbreviations: CR = complete response; PD = progressive disease; PFS = progression-free survival; PR = partial response; RECIST 1.1 = Response Evaluation Criteria in Solid Tumors, Version 1.1; SD = stable disease.

^a Symptomatic deterioration (ie, symptomatic progression that is not confirmed per RECIST 1.1) will not be considered as tumor progression.

^b Adequate tumor assessment per RECIST 1.1 refers to an assessment with one of the following responses: CR, PR, SD, or PD.

^c Refer to the statistical analysis plan for the definition of 2 scan intervals, including any adjustment for scan window.

Time to response (TTR) is defined as the time from the date of start of treatment to the date measurement criteria for confirmed CR or PR (whichever is first recorded) are first met. For patients who are not known to have achieved CR or PR as of the data-inclusion cut-off date, TTR will be censored at the date of the last objective disease assessment prior the date of any subsequent systematic anticancer therapy.

Exploratory Endpoints

As the exploratory objective, the efficacy parameters based on iRECIST will also be analyzed.

Overall response rate (iORR) is measured by the percentage of patients who achieved a complete response (iCR) or partial response (iPR) as their best overall response (iBOR) out of all

treated patients (safety population). The best overall response (iBOR) is defined as the best response across all time point assessments based on RECIST 1.1 and iRECIST.

Progression-free survival (iPFS) should be the date of randomization (the date of first dose for single arm study) to the date at which progression criteria are first met (ie, the date of first iUPD) provided that iUPD or a sequence of consecutive iUPD is confirmed by an iCPD, or the iUPD followed by only iUPDs at subsequent assessments, or no more tumor assessments, or to the death date from any cause in the absence of progressive disease. Patients known to be alive and without the iUPD as mentioned above as of the data inclusion cut-off date for a particular analysis will be censored at the time of the last adequate tumor assessment (a detailed iPFS event/censoring scheme is provided in the table below).

iPFS Event/Censoring Scheme

Situation ^a	Event/Censor	Date of Event or Censor
iUPD confirmed at next assessment (iCPD), or Consecutive iUPD followed by an iCPD	Event	(First) iUPD date
iUPD followed by only iUPD at subsequent assessments and no further tumor assessment available.	Event	First iUPD date of the consecutive iUPDs
iUPD without subsequent assessment	Event	iUPD date
Death	Event	Death date if no iUPD date as in the above 3 situations before death.
No Death and no iUPD or iUPD is followed by iSD/iPR/iCR/	Censored	Date of last adequate tumor assessment per iRECIST, or date of randomization (first dose for single arm study) (whichever is later) ^b
Confirmed iUPD (including all the first 3 Event cases) or death reported after 2 scan intervals following the last adequate tumor scan	Censored	Date of last adequate tumor scan prior to Confirmed IUPD (iCPD) or Death.
No baseline radiologic tumor assessment available	Censored	Date of randomization (first dose for single arm study)
No adequate postbaseline tumor assessment available and death reported after 2 scan intervals following the first dose ^{b, c}	Censored	Date of randomization (first dose for single arm study)

iPFS Event/Censoring Scheme

Abbreviations: “i” indicates immune responses assigned using iRECIST. iCR = complete response; iPR = partial response; iSD = stable disease; iUPD=unconfirmed progression; iCPD=confirmed progression.; iPFS = progression-free survival; RECIST = Response Evaluation Criteria in Solid Tumors;

^a Symptomatic deterioration (ie, symptomatic progression that is not confirmed per iRECIST) will not be considered as tumor progression.

^b Adequate tumor assessment per iRECIST refers to an assessment with one of the following responses: iCR, iPR, iSD, iUPD, or iCPD.

^c Refer to the statistical analysis plan for the definition of 2 scan intervals, including any adjustment for scan window. (new anti-cancer therapy in SAP)

Duration of response (iDoR) is defined as the time from the date measurement criteria for iCR or iPR (whichever is first recorded) are first met until the first date that disease is recurrent or objective progression (as assessed by investigators) is observed, or the date of death from any cause in the absence of objectively determined disease progression or recurrence. Patients known to be alive and without disease progression as of the data inclusion cut-off date for a particular analysis will be censored at the time of the last adequate tumor assessment. iDoR will follow the same censoring scheme as iPFS. iDoR will be analyzed for the treated patients who achieve iCR/iPR as the best of overall response (iBOR).

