### **8.1.2. iRECIST For Confirmation of PD in Clinically Stable Patients and Radiologic PD per RECIST v1.1.**

RECIST v1.1 will be applied as the primary criteria for assessment of tumor response (Eisenhauer et al. 2009). The response to immunotherapy may differ from the typical responses observed with cytotoxic chemotherapy, including the following (Wolchok et al. 2009; Nishino et al. 2013):

- Response to immunotherapy may be delayed.
- Response to immunotherapy may occur after progressive disease by conventional criteria.
- The appearance of new lesions may not represent progressive disease with immunotherapy.

Therefore, to adequately characterize additional patterns of response and progression specific to patients treated with immunotherapy, which cannot be captured using conventional criteria such as RECIST v1.1, alternative measures of tumor assessment have been developed. The iRECIST standard was developed by the RECIST working group for the use of modified RECIST version 1.1 in cancer immunotherapy trials (Seymour et al. 2017).

After initial disease progression defined by RECIST v1.1, iRECIST guidelines will be applied in the following tumor assessments. In iRECIST, any new lesions are categorized as measurable or non-measurable. Up to 5 lesions total (up to 2 per organ) can be selected as new lesion-target (NL-T). All other new lesions will be followed as new lesion-non-target (NL-NT). The NL-T sum of diameters will be calculated and recorded separately from the sum of diameters for target lesions identified at baseline.

Tumor response by iRECIST will be classified as confirmed progression (iCPD), or unconfirmed progression (iUPD), or stable disease or response (iSD/iPR/iCR) at all subsequent imaging. The initial tumor scan showing disease progression by RECIST v1.1 will be assigned as unconfirmed progression (iUPD) for overall response.

Progression is considered confirmed (iCPD), if the previous response status was iUPD and any of the following happens:

- For target lesions: any further increase in the previously identified target lesion sum of diameters by 5mm or more after iUPD.
- For non-target lesions: any further increase in the size of previously identified non-target lesion iUPD (the increase doesn't need to meet RECIST v1.1 criteria for unequivocal progression)
- For new lesions:
  - an increase in the NL-T previously identified as iUPD and increase  $\geq 5$ mm in sum of diameter OR
  - any increase for NL-NT OR

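### As defined in the SAP, iORR drops the confirmation required for ORR as well as admitting responses after progression, so an iORR excess over ORR cannot be attributed to immune-pattern response

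*SAP*

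**What the plan says.** In SAP 6.7, ORR "is defined as the number of patients who achieve a best overall response of complete response (CR) or partial response (PR", taken over the safety population. The next paragraph, on disease control, says how best response is derived: "Two objective status determinations of CR before progression are required for a best response of CR", and "Two determinations of PR or better before progression, but not qualifying for a CR, are required for a best response of PR". Protocol 9.4.3.2 carries the same rule. The time-to-response definition in SAP 6.7 also refers to the date on which "measurement criteria for confirmed CR or PR (whichever is first recorded) are first met".

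For the exploratory immune endpoints, SAP 6.7 counts toward iORR the patients with iCR or iPR "as their best overall response (iBOR) out of all" treated patients. It adds that iBOR "is defined as the best response across all time point assessments based on RECIST 1.1 and iRECIST". The duration endpoint then uses the same classification: "iDoR will be analyzed for the treated patients who achieve iCR/iPR as the best of overall response (iBOR".

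Protocol 9.4.3.3 leaves the iRECIST endpoint definitions to the SAP. Protocol 8.1.2 gives the reason for using iRECIST, including that "Response to immunotherapy may occur after progressive disease by conventional criteria". It sets a confirmation rule for progression (iUPD to iCPD) but describes iCR and iPR by the status at an assessment, with no repeat required. SAP 6.7 plans both ORR and iORR with exact 95% CIs for each arm of Cohorts C and D, and for Cohort E.

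**The concern.** The two rates will be reported for the same patients in the same arms, and the natural use of iORR is to see what iRECIST adds. For that, the two definitions should differ only in how they treat responses after RECIST progression. As worded they also differ in confirmation: a response that fails to confirm is lost to ORR but kept in iORR. A gap between the rates could then come entirely from responses that did not last to a second scan, and a reader could take it for delayed immune activity. Because iDoR is analysed in patients selected by iBOR, the same unconfirmed responders are carried into that endpoint.

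**Working it through.** **Step 1: the plan's own figures.** Protocol 9.2 and SAP 5.2 tabulate Clopper-Pearson 95% intervals for N=20 and N=40. For k responders of n, the lower limit is the 0.025 quantile of Beta(k, n-k+1) and the upper limit is the 0.975 quantile of Beta(k+1, n-k), with a lower limit of 0 when k=0. For 3/20 this gives 0.0321 to 0.3789 (plan: 0.03, 0.38). For 10/40 it gives 0.1269 to 0.412 (plan: 0.13, 0.41). All ten rows of the table reproduce. No tabulated figure depends on the iBOR rule.

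**Step 2: the definitions side by side.**

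| Element | ORR (RECIST 1.1) | iORR as written |
|---|---|---|
| Denominator | Safety population | Safety population |
| Determinations needed | Two | One (best time point) |
| Response after RECIST progression | Does not count | Counts |

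Two elements change together, and only the last row matches the purpose stated in Protocol 8.1.2.

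**Step 3: three patients, reading the iBOR sentence literally.** Scans are every 9 weeks in the first year (Protocol 8.1.1), with repeat imaging 4 to 8 weeks after first progression in clinically stable patients (Protocol 8.1.2).

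| Patient | ORR | iORR as written | iORR with two determinations |
|---|---|---|---|
| A: PR at week 9, progression at week 18, then confirmed | No | Yes | No |
| B: progression at week 9, iPR on the repeat scan, iPR again at the next scan | No | Yes | Yes |
| C: progression at week 9, iPR on the repeat scan only, then progression again | No | Yes | No |

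All three add one patient to iORR minus ORR. Only B is a confirmed response after progression. A has no response after progression at all.

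**Step 4: size.** The documents give no rate at which first responses fail to confirm, so this is an assumption shown as a range. Take 20 patients, 4 of whom have a first PR or CR before any progression, and no response after progression in anyone. iORR is then 4/20.

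| Assumed unconfirmed (of 4) | ORR (95% CI) | iORR (95% CI) | Gap |
|---|---|---|---|
| 0 | 4/20 = 20% (6-44%) | 20% (6-44%) | 0 points |
| 1 (25%) | 3/20 = 15% (3-38%) | 20% (6-44%) | 5 points |
| 2 (50%) | 2/20 = 10% (1-32%) | 20% (6-44%) | 10 points |

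Unrounded limits are 0.057 to 0.437 for 4/20, 0.032 to 0.379 for 3/20 and 0.012 to 0.317 for 2/20. Each unconfirmed response moves the gap by 1/n: 5 points at n=20, 2.5 points at n=40, and 10 points in a monotherapy arm of 10, the size given for the interim in Protocol 9.5 and SAP 6.12.

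**The case against.** The best counter-argument is that the absence of confirmation is an inference. The two-determination rule sits in the disease-control paragraph, not under ORR. If it is carried to ORR as a general rule for best response, it might equally be carried to iBOR, which is said to rest on both RECIST 1.1 and iRECIST. On that reading patient A would not be an iORR responder. The cited iRECIST guideline might also supply a rule, and an abbreviation under the imaging table in Protocol 8.1.2 calls iCR confirmed.

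Some of this stands: the intended rule may be stricter than the wording. But the SAP writes its own sentence for iBOR, and followed as written that sentence takes the best single time point. The abbreviation gives no rule and does not list iPR, and the SAP's own abbreviations omit the word. Even if the RECIST 1.1 part of iBOR imports the confirmation rule, nothing stated covers an iPR reached after iUPD (patient C).

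Three stronger readings are tempting, and the documents do not support them.

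- A reader might infer that iBOR goes on collecting responses after iCPD because no end is stated. Treatment stops at iCPD and no further imaging is required then (Protocol 8.1.2), and imaging after treatment discontinuation runs only until progression, new therapy or withdrawal of consent (Protocol 8.1.1). Few if any scans would follow.
- A reader might infer that patient A is formally outside a DoR analysis set. The SAP defines no such set, and its DoR text does not use the word confirmed.
- A reader might infer that iDoR must come out shorter than DoR. Under the iPFS censoring scheme, which iDoR follows, an iUPD followed by iSD, iPR or iCR is not an event. That can lengthen iDoR, so the net direction is unknown.

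It is also fair that iORR is exploratory, that no formal test of response is planned, and that no passage plans an iORR-minus-ORR contrast.

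**Conclusion.** The concern holds in a limited form. As written, iORR differs from ORR both in confirmation and in admitting responses after RECIST progression, so an excess of iORR over ORR cannot be assigned to immune-pattern response. Unconfirmed responders also enter the iDoR set.

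In the 20-patient illustration the artefact is 5 to 10 percentage points with no response after progression. That rests on the assumed 1 or 2 unconfirmed of 4 first responses, and it is small beside an interval of 6-44% for 4/20. The conclusion about the definitions does not depend on those figures. It rests on taking the iBOR sentence literally and on applying the SAP's best-response rule to ORR, which is the natural reading because ORR is defined through best overall response.

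A reader might infer that the flaw touches the primary result or the decision to expand a cohort. It does not touch the primary ORR, and no decision rule in Protocol 9.5 or SAP 6.12 names iORR. What is at stake is the interpretation of two exploratory endpoints.

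**What to change.** In SAP 6.7, define iBOR with the rule already used for RECIST 1.1: two determinations of iCR for iCR, and two of iPR or better for iPR, using assessments before iCPD. Use this confirmed iBOR for iORR and for selecting the iDoR patients. Report separately the number of patients whose confirmed response was first reached after iUPD, since that is the result specific to iRECIST. If the single-time-point rate is wanted as well, label it unconfirmed and show it beside the confirmed rate.

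Two small clean-ups would help: state the best-response rule where ORR is defined, and reconcile the abbreviation for iCR in Protocol 8.1.2 with the one in SAP 6.7.

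The cost is a few sentences in the SAP and a change to one derivation, with no new data collected. The downside is a slightly lower iORR.

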6.8. Bioanalytical and Pharmacokinetic/Pharmacodynamic Methods

Unless stated otherwise, the Lilly pharmacokineticist will be responsible for the PK/PD analyses.

Selected PK descriptors for LY3475070 (based on actual sampling times), including C_{max} , approximate time of C_{max} (t_{max}), and AUC will be calculated by noncompartmental analysis methods and/or model simulations. As an exploratory analysis, PK descriptor estimates for trough concentrations (C_{min}) at steady state following repeated dose may be evaluated.

In addition, PK parameter estimates for LY3475070 as single agent and in combination with pembrolizumab may be calculated, data allowing. The version of any software used for the analysis will be documented, and the program will meet the Lilly requirements of software validation. It is possible that other validated, equivalent PK software programs may be used if appropriate, warranted, and approved by Global PK/pharmacodynamics management.

PK/pharmacodynamics analyses may be conducted to explore exposure-response relationships between LY3475070 concentrations in systemic circulation and various pharmacodynamic measures as second step if dose-response relationship is positively assessed.

Renal clearance of LY3475070 will be calculated as the ratio of amount excreted/AUC from time 0 to time t (AUC_{0-t}), and will be compared with unbound glomerular filtration rate, estimated using creatinine renal clearance and plasma unbound fraction (F_u) ($F_u \times$ amount of creatinine excreted/creatinine AUC_{0-t}).

